### 9.3 Randomisation, blinding and treatment allocation

This trial is a single-arm study. Therefore no randomisation or blinding will take place. A maximum of 5 patients will be enrolled in phase one of this study. Thereafter, another 10 patients will be enrolled in phase two.

### 9.4 Study procedures

#### 9.4.1 Patient evaluation

Written informed consent will be obtained from patients before study entry. Patients will be screened for meeting all eligibility criteria. At study entry the following data are collected: medical history, characteristics of the primary tumor and metastases, location of a tumor lesion that could be biopsied, co-medication, contraceptive use, pregnancy, ECOG performance score, and a physical examination including vital signs, weight, length and blood pressure. To exclude pregnant women from the study, all WOCBP must undergo a urine pregnancy test (beta hCG) before study entry. To

exclude patients with an acute or chronic hepatitis infection, HBV sAg and HCVantibody will be determined. In addition, blood tests are acquired (e.g. complete blood count and blood chemistry), which are part of the regular treatment with nivolumab.

#### 9.4.2 PET procedure and quantification of tracer uptake

[figure not shown]
[figure not shown]
In phase one, the tracer kinetics will be measured in order to determine the optimal tracer distribution time and to evaluate which simplified method is best suited for the quantitative analysis of the tracer uptake. For this purpose, 5 patients will undergo an extended PET acquisition protocol, both at baseline and after 6 weeks of treatment with immunotherapy. Immediately after injection of the tracer a dynamic PET scan will be acquired of the chest (single bed position; 60 minutes). The dynamic PET scan will be followed by two total body PET scans (head to toe; 12 bed positions, 3 minutes per bed position). The first total body PET starts at 60 minutes after tracer injection (i.e. immediately after the dynamic PET scan). After this scan (ca. 90-100 minutes after tracer injection), the patient can shortly leave the PET camera. An additional total body scan will be performed at 120 minutes after tracer injection. The two total body scans will be used to quantify tracer uptake in tumors and tumor contrast throughout the body in order to establish the optimal time point for imaging. If during this phase of the study either one of the two total body PET scans seems obsolete due to low tracer availability, small differences between both scans or whatever other reason, one scan will be omitted to minimize burden in the following patients.

In phase two, a single PET-scan will be performed at baseline and after six weeks of treatment at the optimal time point after tracer injection as determined in phase one. Both scans will be accompanied by a low-dose or diagnostic CT-scan for anatomic reference purposes. The scans will be performed one hour or two hours after tracer injection, depending on the optimal time of tracer injection as established in phase I.

Before the start of the imaging procedure, a venous catheter is placed in one arm and patients will be injected with approximately 200 MBq (0,63mL) [18F]PD-L1. Patients will be asked to drink 1 liter of water to promote the renal clearance of unbound tracer from the circulation in order to enhance signal to background ratio. Prior to scanning, patients will be asked to go to the toilet to empty their bladder in order to reduce the radiation burden to the patient and prevent high bladder uptake on the PET scan.

Vital signs (blood pressure and heart rate) will be measured before, 10 minutes after the injection of [18F]PD-L1 and directly after the PET-CT scan. Blood samples will be taken before and after each PET-CT scan to analyze complete blood count and blood chemistry.

During the PET-scan, multiple venous samples will be taken to assess tracer metabolism.

**A.****B.**

\*Scan sequence will be determined based on phase one of this study

*Fig.2 – A: Detailed overview of the procedures in phase one of the study. Patients will be scanned both at baseline and after six weeks of treatment during a two hour scan protocol. B: Detailed overview of the procedures in phase two of the study. Again, patients will be scanned both at baseline and after six weeks of therapy. At both time points, only a single PET-scan will be performed. To assess PD-L1 expression by IHC a biopsy will be taken after both PET-scans.*

For quantification of tracer uptake, the investigator visually identifies tumor lesions on a PET or CT scan and determines a region-of-interest (ROI) around these lesions.  $[^{18}\text{F}]$ PD-L1-uptake in these ROI's will be corrected for body weight and injected dose and quantified as standardized uptake value

( $SUV_{max}$  and  $SUV_{mean}$ ). The absolute tracer uptake will be assessed both at baseline and six weeks after treatment initiation.

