#### 9.4.3 CT scan

During phase two, each PET scan will be accompanied by a diagnostic CT scan. The CT scans performed at baseline of treatment with anti-PD1 treatment are part of care as usual. If a diagnostic CT scan has been performed shortly before to inclusion ( $\leq 2$  weeks) this will not be repeated. CT imaging consists of examination of chest, abdomen and pelvis. Response to treatment of tumor lesions will be evaluated according to the RECIST 1.1 criteria.

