#### 9.4.5 Biopsy

In phase two of the study at least one biopsy sample will be collected from an accessible tumor lesion after each PET scan. If possible, these tissue samples will be obtained from the same tumor lesions at baseline and after 6 weeks of treatment. Ideally biopsies will be taken from both [18F]PD-L1 PET positive as well as negative lesions within the same patient. Determination of the biopsy site will be based on tumor localization on previous diagnostic imaging studies and will be performed according to current safety criteria. A biopsy will be performed under local anesthetics and ultrasonographic or CT-guidance. Biopsy material will be FFPE.

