### 11.1 Primary study parameter(s)

Tracer pharmacokinetics and the optimal time for scanning will be determined from the data obtained by the serial PET scans in first 5 patients. Output parameters are the radiation absorbed dose to major organs, the effective dose equivalent for patients, the recommended maximum injected dose for  $[^{18}\text{F}]$ PD-L1 and the optimal time point for scanning after tracer administration.

PD-L1 expression in melanoma tumor lesions will be quantified by measuring tracer uptake in tumor lesions. Tracer uptake will be corrected for body weight and injected dose and quantitatively assessed as standardised uptake value (SUVmean with associated standard deviation and SUVmax), which is calculated using the formula: [tissue activity concentration (MBq/g)]/[(injected dose (MBq)/body weight (g)]. SUV will be calculated for all predefined ROI's on the PET-CT scan at baseline. On the PET-CT scan at week 6 of treatment, SUV will be determined for all lesions detected at baseline as well as all newly detected tumor lesions.

Tumor uptake of  $[^{18}\text{F}]$ PD-L1 will be correlated with the amount of PD-L1 expression of melanoma cells and PD-1 and PD-L1 expression on tumor infiltrating immune cells in melanoma lesions. PD-L1 and PD1 expression will be measured by immunohistochemistry. Results of immunohistochemical staining will be described as a semi-quantitative score using the percentage of positive cells (continuous variable), intensity and pattern of staining (discrete variable). This semi-quantitative score will then be correlated to SUV of the corresponding lesion on the  $[^{18}\text{F}]$ PD-L1 PET. Correlation will be expressed as a Pearson/Spearman correlation coefficient depending on distribution of data. Results will be displayed in graphs.

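### Section 9.4.2 lets the tracer PET itself admit lesions to the set in which uptake and SUV change are measured; this can distort both, by an amount the documents do not allow one to fix

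*Combined protocol and SAP*

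**What the plan says.** The quantification text of section 9.4.2 (after Fig. 2) states that "the investigator visually identifies tumor lesions on a PET or CT scan and determines a region-of-interest (ROI) around these lesions". It gives no uptake threshold, reading order or deciding modality, and it does not mention MRI.

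Section 11.1 adds that "SUV will be calculated for all predefined ROI's on the PET-CT scan at baseline", without saying how, when or on which images the regions were defined. For week 6, "SUV will be determined for all lesions detected at baseline as well as all newly detected tumor lesions". Section 9.3 states that there is no blinding.

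On the accompanying imaging:
- The Summary combines PET in both phases with a low-dose or diagnostic CT of chest, abdomen and pelvis and an MRI of the brain.
- For phase two, section 9.4.2 says "Both scans will be accompanied by a low-dose or diagnostic CT-scan for anatomic reference purposes", while section 9.4.3 says "During phase two, each PET scan will be accompanied by a diagnostic CT scan". These two need to be reconciled. Section 9.4.3 also says "The CT scans performed at baseline of treatment with anti-PD1 treatment are part of care as usual".
- The phase-one total body PET runs from head to toe (9.4.2).
- Inclusion criterion 4 requires a brain lesion measurable on MRI in every subject.

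The lesion set feeds two analyses. Sections 3.2 and 9.2 name variability of uptake between and within patients. Section 11.2 takes the per-lesion SUV difference between scans, examines its heterogeneity and relates it to response.

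**The concern.** The tracer under evaluation helps choose the lesions in which it is measured. A lesion seen on CT enters whatever its uptake; a lesion not seen on CT enters only when its uptake is high. That second group is selected on the outcome variable.

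For some lesions the CT route is closed or nearly so. Brain lesions are imaged by MRI, which the rule leaves out, and head CT replaces MRI only where MRI is contraindicated (9.4.4). Limb or neck lesions can lie inside the PET field and outside the CT field.

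Two results are at stake: the spread of uptake, which is the secondary objective, and the mean SUV change. Lesions chosen because their first reading was high tend to read lower the second time, even if nothing has changed. Newly detected week-6 lesions raise a further question. Section 11.1 gives no rule for their baseline SUV, so the difference in section 11.2 is undefined for them.

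**Working it through.** The plan gives no figure to reproduce: no SUV standard deviation, between-scan reliability, detection rate or lesion count. The check uses a model whose inputs are all assumptions.

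**Model.** Baseline SUV X is standard normal (in SD units) and true uptake does not change. The between-scan correlation is r. A share q of lesions, those with X > t, is visible on PET. A share c is visible on CT, independently of X. A lesion is included if either scan shows it.

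**Formulas**, with φ the normal density at t:
- Share included: w = q + (1 − q)c
- Mean of included lesions: m = (1 − c)φ/w
- SD ratio: k = √{[(1 − c)(q + tφ) + c]/w − m²}
- Spurious mean change: −(1 − r)m

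**Example: q = 0.7, c = 0.5, r = 0.8.** Here t = −0.524, φ = 0.348 and w = 0.7 + 0.3 × 0.5 = 0.85.
- m = 0.5 × 0.348/0.85 = 0.205
- k = √{[0.5 × (0.7 − 0.182) + 0.5]/0.85 − 0.042} = √0.851 = 0.92
- change = −0.2 × 0.205 = −0.041 SD

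**Range** (each cell for q = 0.5 / 0.7 / 0.9):

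| CT-visible share c | SD ratio of uptake | Mean change, r = 0.8 | Mean change, r = 0.6 |
|---|---|---|---|
| 0 (PET the only route) | 0.60 / 0.70 / 0.84 | −0.16 / −0.10 / −0.04 | −0.32 / −0.20 / −0.08 |
| 0.5 | 0.96 / 0.92 / 0.93 | −0.053 / −0.041 / −0.018 | −0.106 / −0.082 / −0.037 |
| 0.8 | 0.996 / 0.978 / 0.976 | −0.018 / −0.015 / −0.007 | −0.035 / −0.030 / −0.014 |

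A simulation of 2,000,000 lesions agreed with the mean-change formula to within 0.002.

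**Direction.** If few lesions are PET-visible (q = 0.1 to 0.3) and c = 0.3 to 0.8, the SD ratio is 1.01 to 1.15, so the spread is inflated. The mean change is negative for every c < 1 and r < 1. If lesions visible on PET at either scan were admitted and measured at both, it would be zero.

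**Spread of the SUV difference.** Section 11.2 analyses this quantity. Its SD ratio is √{[(1 − r)²k² + 1 − r²]/[2(1 − r)]}. Take the extreme case in which PET alone selects and the lowest 20 to 40% of lesions are missed (k = 0.764 to 0.650):
- k = 0.764, r = 0.9: √[(0.0058 + 0.19)/0.2] = 0.99
- k = 0.650, r = 0.6: √[(0.0676 + 0.64)/0.8] = 0.94

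**After the fix.** Admission no longer depends on X. In this model the listed lesions have an SD ratio of 1.00 and a spurious change of 0 for every q and r.

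**The case against.** The strongest reply is that the rule says PET *or* CT. A CT-visible lesion enters regardless of uptake, so the low tail is not simply cut off. This stands, and it is why the effects in the lower rows of the table are small.

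Other replies also carry weight:
- Every baseline lesion is re-measured at week 6 (11.1), so none drops out because its uptake falls.
- Section 11.2 relates SUV change to response, and a downward shift common to responding and non-responding lesions largely cancels there.
- The shift is small beside sampling error. With 10 independent units (for illustration) and r = 0.8, the standard error of the mean change is √[2(1 − 0.8)]/√10 = 0.20 SD.
- Biopsy sites come from previous diagnostic imaging, and section 9.4.5 says "Ideally biopsies will be taken from both [18F]PD-L1 PET positive as well as negative lesions within the same patient". The primary SUV-IHC correlation is therefore less exposed.
- The study is exploratory and mainly descriptive (section 11).

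A reader might also infer that the two phases are selected quite differently, since section 9.4.3 prescribes diagnostic CT for phase two only. The documents do not support a sharp contrast. The Summary gives CT and brain MRI in both phases, section 9.4.2 allows low-dose CT in phase two as well, and the baseline CT is usual care.

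None of these replies closes the gap. Calling the regions predefined names neither a modality nor an order, and the CT route does not serve brain lesions or lesions outside the CT field.

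**Conclusion.** The gap is real: uptake can decide which lesions are measured, and nothing in the plan prevents it. For lesions that enter through PET alone, this can distort the heterogeneity estimate in either direction and builds a downward shift into the mean SUV change of baseline-selected lesions.

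The effect is probably small where CT detects most lesions: an uptake SD ratio of about 0.92 to 1.00 and a shift of about −0.01 to −0.05 SD, for c = 0.5 to 0.8, q = 0.5 to 0.9 and r = 0.8. It is larger where PET is the only route, with a ratio of 0.60 to 0.84 and a shift of −0.04 to −0.32 SD for r = 0.8 to 0.6. These ranges rest on assumed q, c and r, normal SUV, and CT visibility unrelated to uptake. The documents supply none of these.

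A reader might go further and conclude that the rule must shrink the spread of uptake by a quarter or more and produce a sizeable fall in SUV. That requires PET to be the sole selector, which is not what section 9.4.2 says. Even then the spread of the SUV difference would be only 0.94 to 0.99 of its true value in the case shown. Nor do the documents support a claim that the primary SUV-IHC result is materially biased.

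**What to change.** In section 9.4.2, for both phases:
- Have the existing reader list all lesions on the available CT and brain MRI before the tracer PET is opened. The usual-care baseline CT can serve in phase one.
- Copy those regions to the PET and report SUV for each, even where no uptake is visible.
- Record the modality on which each lesion was found.

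In sections 11.1 and 11.2, make this CT/MRI-defined list the main set for the heterogeneity and SUV-change analyses. Report PET-only lesions and newly detected week-6 lesions separately, with a sensitivity analysis that includes them. State how a baseline SUV is obtained for the week-6 lesions.

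PET-only lesions should not simply be dropped, since that would lose lesions outside the CT field in a study that aims at whole-body information.

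The cost is protocol wording and a fixed reading order, with no extra scan. The drawback is that lesions outside the CT/MRI field appear only in the separate list and the sensitivity analysis. The order has to be fixed before the scans are read, because a list cannot be made independent of a PET the reader has already seen.

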#### 9.4.3 CT scan

During phase two, each PET scan will be accompanied by a diagnostic CT scan. The CT scans performed at baseline of treatment with anti-PD1 treatment are part of care as usual. If a diagnostic CT scan has been performed shortly before to inclusion ( $\leq 2$  weeks) this will not be repeated. CT imaging consists of examination of chest, abdomen and pelvis. Response to treatment of tumor lesions will be evaluated according to the RECIST 1.1 criteria.

#### 9.4.4 MRI scan

During phase two, each PET scan will also be accompanied by a MRI scan of the brain. These MRI scans are also part of regular care at baseline of treatment with anti-PD1 treatment. If a recent brain MRI scan has been performed prior to inclusion ( $\leq 2$  weeks) this will not be repeated at baseline. Before the MRI scan will be performed, gadolinium will be administrated intravenously which acts as a contrast agent. In subjects with a contraindication for an MRI scan, this could be replaced by a contrast-enhanced head CT scan.

#### 9.4.5 Biopsy

In phase two of the study at least one biopsy sample will be collected from an accessible tumor lesion after each PET scan. If possible, these tissue samples will be obtained from the same tumor lesions at baseline and after 6 weeks of treatment. Ideally biopsies will be taken from both [18F]PD-L1 PET positive as well as negative lesions within the same patient. Determination of the biopsy site will be based on tumor localization on previous diagnostic imaging studies and will be performed according to current safety criteria. A biopsy will be performed under local anesthetics and ultrasonographic or CT-guidance. Biopsy material will be FFPE.

#### 9.4.6 Immunohistochemistry

Immunohistochemistry will be performed on FFPE tumor blocks mounted on 3-aminopropyltriethoxysilane-coated glass slides. To determine PD-L1 and PD1 expression on melanoma cells and tumor infiltrating immune cells respectively, these slides will be stained with anti-PD-L1 and anti-PD1 monoclonal antibodies. For quantitative scoring of positively stained cells,

the percentage of positive cells, the intensity of staining and the pattern of staining will be accounted for.

### **9.5 Withdrawal of individual subjects**

Subjects can leave the study at any time for any reason if they wish to do so without any consequences. The investigator can decide to withdraw a subject from the study for urgent medical reasons.

### **9.6 Replacement of individual subjects after withdrawal**

Subjects that withdraw from the study will be replaced in order to achieve the number of patients needed for the study endpoints; see 'sample size calculation'.

### **9.7 Premature termination of the study**

Premature termination will only be applied when serious unforeseen adverse events are detected which could be clearly attributed to the investigational product, and which prompt a premature termination of the study.

## 10. SAFETY REPORTING

### 10.1 Section 10 WMO event

In accordance to section 10, subsection 1, of the WMO, the investigator will inform the subjects and the reviewing accredited METC if anything occurs, on the basis of which it appears that the disadvantages of participation may be significantly greater than was foreseen in the research proposal. The study will be suspended pending further review by the accredited METC, except insofar as suspension would jeopardise the subjects' health. The investigator will take care that all subjects are kept informed.

### 10.2 AEs, SAEs and SUSARs

#### 10.2.1 Adverse events (AEs)

AEs are defined as any undesirable experience occurring to a subject during the study, whether or not considered related to the investigational product. All AEs reported spontaneously by the subject or observed by the investigator or his staff will be recorded.

#### 10.2.2 Nonserious adverse events

A nonserious adverse event is an AE not classified as serious. The collection of nonserious AE information should begin at initiation of study drug. All nonserious AEs (not only those deemed to be treatment-related) should be collected continuously during the treatment period and for a minimum of 100 days following the last dose of study treatment.

Nonserious AEs should be followed to resolution or stabilization, or reported as SAEs if they become serious. Follow-up is also required for nonserious AEs that cause interruption or discontinuation of study drug and for those present at the end of study treatment as appropriate.

#### 10.2.3 Serious adverse events (SAEs)

All SAEs reported spontaneously by the subject or observed by the investigator or his staff will be recorded according to CTCAE v4.0. A SAE is any experience that suggests a significant hazard, contraindication, side effect or precaution. It is any AE that at any dose fulfills at least one of the following criteria:

- results in death;
- is life threatening (at the time of the event);
- requires hospitalisation or prolongation of existing inpatients' hospitalisation;

- results in persistent or significant disability or incapacity;
- is a congenital anomaly or birth defect;
- is a potential drug induced liver injury (DILI);
- is a suspected transmission of an infectious agent (eg, pathogenic or nonpathogenic) via the study drug;
- is a pregnancy, overdose, or secondary cancer;
- Any other important medical event that may not result in death, be life threatening, or require hospitalization, may be considered a serious adverse experience when, based upon appropriate medical judgement, the event may jeopardize the subject or may require an intervention to prevent one of the outcomes listed above.

Medical and scientific judgment should be exercised in deciding whether expedited reporting to the sponsor is appropriate in other situations, such as important medical events that may not be immediately life-threatening or result in death or hospitalization but may jeopardize the patient or requires intervention to prevent one of the outcomes listed in the definitions above. These situations should usually be considered serious. Examples of such events are intensive treatment in an emergency room or at home for allergic bronchospasm; blood dyscrasias or convulsions that do not result in hospitalization; or development of drug dependency or drug abuse. An unexpected Adverse Event is one, the nature or severity of which is not consistent with the applicable product information.

The causal relationship to study drug is determined by a physician and should be used to assess all adverse events (AE). The causal relationship can be one of the following:

- Related: There is a reasonable causal relationship between study drug administration and the AE.
- Not related: There is not a reasonable causal relationship between study drug administration and the AE.

The term "reasonable causal relationship" means there is evidence to suggest a causal relationship.

The term severe is a measure of intensity, thus a severe adverse event is not necessarily serious. For example, nausea of several hours' duration may be rated as severe, but may not be clinically serious. Following the subject's written consent to participate in the study, all SAEs, whether related or not related to study drug, must be collected, including those thought to be associated with protocol-specified procedures. All SAEs must be collected that occur within 100 days of discontinuation of dosing.

In addition, a SAE that occurs after this time, if considered related to test "drug", should be reported. Such preliminary reports will be followed by detailed descriptions later which will include copies of hospital case reports, autopsy reports and other documents when requested and applicable. For

SAEs, the following must be assessed and recorded on the adverse events page of the Case Report Form: intensity, relationship to test substance, action taken, and outcome to date.

The sponsor will report the SAEs through the web portal *ToetsingOnline* to the accredited METC that approved the protocol, within 15 days after the sponsor has first knowledge of the serious adverse reactions.

SAEs that result in death or are life threatening should be reported expedited. The expedited reporting will occur not later than 7 days after the responsible investigator has first knowledge of the adverse reaction. This is for a preliminary report with another 8 days for completion of the report.

Besides reporting to the accredited METC, all SAE's that occur following the subject's written consent to participate in the study through 100 days of discontinuation of dosing must be reported to the sponsor BMS Worldwide Safety. (email: [[contact]](mailto:[contact]); [contact])

All SAEs must be collected that occur during the screening period. If applicable, SAEs must be collected that relate to any protocol-specified procedure (eg, a follow-up skin biopsy). The investigator should report any SAE that occurs after these time periods that is believed to be related to study drug or protocol-specified procedure.

SAEs, whether related or not related to study drug, and pregnancies must be reported to BMS within 24 hours. SAEs must be recorded on BMS or an approved form; pregnancies on a Pregnancy Surveillance Form.

If only limited information is initially available, follow-up reports are required. (Note: Follow-up SAE reports should include the same investigator term(s) initially reported.)

If an ongoing SAE changes in its intensity or relationship to study drug or if new information becomes available, a follow-up SAE report should be sent within 24 hours to the BMS (or designee) using the same procedure used for transmitting the initial SAE report.

All SAEs should be followed to resolution or stabilization.

